6.3. OVERALL STUDY EVALUATIONS AND MEASUREMENTS

6.3.1. EFFICACY

For the interim analysis, efficacy will be tested via T-tests of percent change in wound size using an intention to treat (ITT) approach as well as a per protocol analysis. For the final analysis, efficacy will be tested via T-tests of percent change in wound size using an intention to treat (ITT) approach as well as a per protocol analysis. Stratification of efficacy results by smoking status and study ulcer Stage will be conducted, although the results are expected to be similar given the stratified randomization.

For the interim analysis and final analyses, secondary analyses will include Kaplan-Meier analysis to estimate time to complete wound closure, and comparisons of infection status of the ulcer. Number and health care resource utilization (wound-related) will be tallied and compared between Microcyn and saline. Other secondary analyses may include linear and logistical regression to estimate the impact of patient characteristics on study endpoints, with special emphasis on variables that affect healing times, such as diabetes. If there are sufficient number of patients with multiple wounds, a mixed effects linear model

will be run, handling the patient as a group that has been randomized to a treatment to determine if there are any spillover effects of treating one wound with Microcyn.

If the interim analysis indicates that the difference in estimated time to complete wound closure between the two populations is 26% or higher at a significance level of $p < 0.05$, the study will be halted early for success.

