
 – Patient has any wound that at enrollment is scheduled for surgical closure within 14 days – Use of any immunosuppressant medications (for example, cyclosporine, methylprednisolone, prednisone, methotrexate, alefacept, or infliximab) within 30 days of screening – Is unable to fully comply with the study requirements; for example, if the wound is in a place that the patient cannot reach him/herself and as such requires a caregiver to apply the study product, if the patient does not have consistent twice daily access to a caregiver, this patient would be ineligible for the study – Any condition or situation which, in the Investigator’s opinion, puts the subject at significant risk, could confound the study results, or may interfere significantly with the subject’s participation in the study – Patient is medically unstable or has a life expectancy of less than 12 months – Patient is pregnant – Patient is a woman of child-bearing potential and does not consent to or receive a screening urine pregnancy test prior to study enrollment – Current enrollment in an investigational drug or device study or participation in such a study within the last 30 days prior to Baseline (Week 0) 	

Name of Sponsor/Company:	Oculus Innovative Sciences, Inc.
Name of Finished Product:	Microcyn [®] Skin and Wound Care with preservatives (“Microcyn”)
Name of Active Ingredient:	N/A
Test Article, Dose, and Mode of Administration:	
Microcyn [®] Skin and Wound Care with preservatives, applied twice daily, topical administration	
Statistical Analyses:	
Efficacy Analyses:	
Efficacy will be tested via T-tests of percent change in wound size using an intention to treat (ITT) approach as well as a per protocol analysis. Secondary analyses will include Kaplan-Meier analysis to estimate time to complete wound closure, and may include linear and logistical regression to estimate the impact of patient characteristics on study endpoints, with special emphasis on variables that affect healing times, such as diabetes and smoking status. The efficacy population will include all patients entered into the study.	
Safety Analyses:	
Safety analyses will be conducted via Fischer’s exact tests, chi-square, and t-tests, as applicable. The safety population will include all subjects exposed to the any study product (Microcyn or saline) who have provided any post-treatment safety information.	
Sample Size Justification:	

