The sample is a convenience sample of 80 patients.	

LIST OF ABBREVIATIONS AND DEFINITIONS OF TERMS

Abbreviation	Definition
AE	Adverse Event
ASIA	American Spinal Cord Injury Association
CFR	Code of Federal Regulations
CTEP-	Cancer Therapy Evaluation Program – Common Terminology Criteria for
FDA	Food and Drug Administration
GCP	Good Clinical Practices
HHS	Health and Human Services
ICH	International Conference on Harmonisation
IEC	Independent Ethics Committee
IRB	Institutional Review Board
ITT	Intention To Treat
MedDRA	Medical Dictionary for Regulatory Activities
NPUAP	National Pressure Ulcer Advisory Panel
PUSH	Pressure Ulcer Scale for Healing
SAE	Serious Adverse Event
SAS	Statistical Analysis Software
SOP	Standard Operating Procedure
UPT	Urine Pregnancy Test
US	United States
WOCBP	Woman of Childbearing Potential

COVER PAGE ERROR! BOOKMARK NOT DEFINED.

SIGNATURE PAGE 2

INVESTIGATOR'S AGREEMENT 3

PROTOCOL SYNOPSIS..... 4

LIST OF ABBREVIATIONS AND DEFINITIONS OF TERMS..... 9

1. INTRODUCTION AND BACKGROUND..... 12

 1.1. STUDY RATIONALE 15

 1.2. DOSE RATIONALE 16

 1.3. STUDY OBJECTIVE..... 16

 1.4. CLINICAL HYPOTHESES..... 16

2. STUDY DESIGN..... 17

 2.1. OVERALL DESIGN..... 17

 2.1.1. *Structure*..... 17

 2.1.2. *Duration* 17

 2.1.3. *Controls*..... 17

 2.1.4. *Dosage/Dose Regimen*..... 17

 2.2. TEST ARTICLE 17

 2.3. STUDY POPULATION 17

 2.4. ELIGIBILITY CRITERIA..... 17

 2.4.1. *Informed Consent and Authorization to Release Health Information*..... 17

 2.4.2. *Inclusion Criteria*..... 19

 2.4.3. *Exclusion Criteria*..... 19

3. STUDY PROCEDURES AND METHODS..... 21

 3.1. SUBJECT ENTRY PROCEDURES..... 21

 3.2. SCHEDULE OF VISITS AND PROCEDURES 21

 Table 1: Schedule of Visits and Procedures 21

 3.2.1. *Baseline Visit* 21

 3.2.2. *follow-up visits (Weeks 4, 8, 12, 16, 20)*..... 24

 3.2.3. *subject application instructions*..... 26

 3.2.4. *subject restrictions* 26

 3.2.5. *Discontinuation/Withdrawal Procedures*..... 26

 3.3. VARIATION FROM SCHEDULED VISIT DAYS..... 27

 3.4. SAFETY ASSESSMENTS 27

 3.4.1. *adverse events*..... 27

 3.5. EFFICACY ASSESSMENTS..... 27

 3.5.1. *Time to wound closure*..... 27

 3.6. SCREEN FAILURES..... 27

 3.7. PROTOCOL DEVIATIONS..... 28

4. PROHIBITED MEDICATIONS AND TREATMENTS..... 29

Table 2: Prohibited Medications and Treatments	29
5. EVALUATION OF ADVERSE EVENTS.....	30
5.1. DEFINITIONS.....	30
5.1.1. Adverse Event Severity Grades	32
5.1.2. Study product Causality	33

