The numbers above represent “nodes” of care with nodes 1-4 representing the four basic components of an effective pressure ulcer care plan: (Node 1) necrotic tissue debridement; (Node 2) initial wound cleansing and repeated cleansing with each dressing change; (Node 3), prevention, diagnose and treatment of infection; and (Node 4), using a wet ulcer dressing that keeps surrounding tissue dry. Nodes 5-14 as shown above represent

assessment and reassessment of the healing strategy and its outcome(s) to ensure optimal healing.

Spinal cord injured patients are an especially vulnerable population for pressure ulcers because of both the immobility rendered by resultant paralysis and of impaired sensation. The National Spinal Cord Injury Statistical Center (NSCISC) estimates that between 231,000 and 311,000 Americans are living with a spinal cord injury (SCI), with approximately 12,000 new cases each year.⁴ As a result of increased research and interest, remarkable progress has been made in improving the quality of life and life expectancy for SCI patients. Secondary complications, however, continue to challenge individuals living with SCI and their caregivers. Pressure ulcers, in particular, “remain the single most important medical complication in terms of loss of time in educational or vocational pursuits, increased hospital stay and resulting financial expenditures.”⁵ In patients with paraplegia, pressure ulcers are the leading cause of rehospitalization;⁶ across injury levels, sepsis from pressure ulcers and genitourinary tract infections are the leading cause of death in Veterans with SCI.⁷

Recent cost estimates on treating pressure ulcers in SCI patients indicate a range of \$2,000 to \$70,000 per wound, with an annual aggregate cost of approximately \$2.2 to \$3.6 billion in the United States alone.⁸ In a retrospective study reviewing medical records of veterans with spinal cord injury, it was found that over 50% of pressure ulcers did not fully heal over the three-year study period, with over 70% of Stage IV ulcers remaining unhealed despite surgeries and multiple hospitalizations.⁹

⁴ *Spinal Cord Injury Facts and Figures at a Glance*, National Spinal Cord Injury Statistical Center, Birmingham, Alabama, February 2010, <https://www.nscisc.uab.edu>.

⁵ Jackson, AB., *Secondary Conditions of Spinal Cord Injury*, Spinal Cord Injury Network, <http://www.spinalcord.uab.edu/show.asp?durki=32106>.

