1.3. STUDY OBJECTIVE

The primary objective is to compare percentage change in wound size in patients with at least one Stage III or Stage IV pressure ulcer in subjects treated with Microcyn versus saline.

The secondary objective is to compare other indicators of wound healing such as time to complete wound closure, elimination of signs of wound infection and to investigate the impact of treatment with Microcyn on subject health care resource utilization (wound-related).

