3.2.1. BASELINE VISIT

The following procedures must be performed and recorded at the Baseline (Week 0) visit, gathered from the patient in the clinic unless otherwise specified:

1. Review study procedures and information regarding the study with the subject and obtain written informed consent
2. Review eligibility criteria; inclusion/exclusion (see Section 2.4.2 and Section 2.4.3)
3. For women of childbearing potential, obtain screening urine pregnancy test
4. Obtain demographic information and relevant medical/social history (from chart)
 - a. *Demographics*: age, race (Caucasian, African-American, Hispanic, mixed race, other), gender, marital status, employment status, education (\leq high school, some college, \geq college), insurance status (Medicare, Medicaid, private insurance, other, no insurance) including identification of whether plan is managed care or fee-for-service.
 - b. *Medical/social*
 1. Height (feet/inches), weight (lbs)
 2. Smoking status (current, former, never)
 3. Alcohol (drink every day, a few drinks per week, a few drinks per month, seldom drink, abstain)
 4. Diabetes (yes, no) (from chart)
 5. Injury information (from chart)
 - a) Date of injury
 - b) Injury level (C1-8, T1-12, L1-5)
 - c) American Spinal Cord Injury Impairment Scale (ASIA) score (if known)
 - a. ASIA A – complete, no motor or sensory function is preserved in sacral segments S4-S4
 - b. ASIA B – incomplete, sensory but not motor function is preserved below the neurological level and includes the sacral segments S4-S5.
 - c. ASIA C – incomplete, motor function is preserved below the neurological level, and more than half of key muscles below the neurological level have a muscle grade less than 3.

- d. ASIA D - Incomplete: Motor function is preserved below the neurological level, and at least half of key muscles below the neurological level have a muscle grade of 3 or more.
 - e. ASIA E = Normal: motor and sensory functions are normal.
 - 6. Current antibiotic use
 - 7. Results of any potentially relevant clinical laboratory tests, e.g., albumin, hemoglobin, performed at or within 14 days of baseline.
- 5. Patients will be stratified according to (1) smoking status; and (2) study ulcer Stage. Following stratification, patients will be randomized to study product (Microcyn or sterile saline). Document study pressure ulcer.

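### The primary t-test does not use the randomisation strata (smoking status, ulcer Stage); if they predict healing it gives up power, by an amount the documents do not let us fix

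*Combined protocol and SAP*

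**What the plan says.** The objective in section 1.3 reads: "The primary objective is to compare percentage change in wound size". Wound size is volume (section 3.2.1), and tests are two-sided at 5% (section 6.1). The test named for the final analysis is: "For the final analysis, efficacy will be tested via T-tests of percent change in wound size using an intention to treat (ITT) approach", with a per-protocol version alongside. The synopsis agrees: "Efficacy will be tested via T-tests of percent change in wound size". Neither place names a covariate.

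On randomisation, section 3.2.1 says: "Patients will be stratified according to (1) smoking status; and (2) study ulcer Stage". Smoking is recorded at three levels (current, former, never), but the plan does not say which levels form the strata. It also gives no allocation ratio, block size or other method of balancing within strata.

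Section 6.3.1 adds that efficacy results will be stratified by the two factors, without giving a model, a weighting or a pooled test. Regression on patient characteristics is secondary and optional. The synopsis describes it as "with special emphasis on variables that affect healing times, such as diabetes and smoking status"; section 6.3.1 gives only diabetes as its example.

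On size, the synopsis says: "The sample is a convenience sample of 80 patients". No power, effect size or SD is given, and section 3.2.5 says that withdrawals are not replaced.

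**The concern.** A design stratifies on factors thought to affect outcome. If they do, they account for part of the spread in percent change. A two-group t-test leaves that part in its error term, so the comparison is less precise than the design allows. If allocation was also balanced within strata, the true variability of the arm difference is smaller than the t-test's standard error, and the test rejects less often than its nominal 5%.

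The plan's own text suggests that the strata may matter. The synopsis counts smoking among the variables that affect healing times. For Stage the support is indirect: the introduction cites a retrospective study in which over 50% of all pressure ulcers did not fully heal over three years, "with over 70% of Stage IV ulcers remaining unhealed despite surgeries and multiple hospitalizations". That is complete healing over three years, not percent change over 24 weeks.

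At stake is efficiency, not validity. With a sample not sized by any power calculation and no replacement of withdrawals, nothing in the plan offsets avoidable imprecision in the primary comparison.

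**Working it through.** **Inputs from the documents.** 80 patients, two-sided 5%, two stratification factors (up to 3 x 2 = 6 strata), t-test of percent change. The plan has no power figure to reproduce.

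**Assumptions.** 1:1 allocation (40 per arm); R2, the share of variance in percent change explained by the strata, from 0 to 0.30. For scale, the effect is set at the standardised difference detectable with 80% power: (1.96 + 0.84) x sqrt(2/40) = 2.80 x 0.2236 = 0.626.

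**Formula, allocation balanced within strata.** The true SE is the nominal SE times sqrt(1 - R2). With k = 1/sqrt(1 - R2):

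- t-test type I error = 2 x Phi(-1.96k)
- t-test power = Phi(0.84k)
- adjusted power = Phi(2.80k - 1.96)

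| Strata R2 | k | t-test type I error | t-test power | Adjusted power |
|---|---|---|---|---|
| 0.05 | 1.03 | 4.4% | 81% | 82% |
| 0.10 | 1.05 | 3.9% | 81% | 84% |
| 0.20 | 1.12 | 2.8% | 83% | 88% |
| 0.30 | 1.20 | 1.9% | 84% | 92% |

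**Simulation, normal outcome, N = 80, effect 0.626.** The formula ignores lost degrees of freedom and chance imbalance, so it was checked by simulation. Entries are power, t-test -> adjusted.

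| Strata R2 | Strata only, blocks of 4 | Strata plus an unrelated baseline term, blocks of 4 | Same model, simple randomisation |
|---|---|---|---|
| 0 | 79.3 -> 79.2 (-0.1) | 79.8 -> 79.2 (-0.6) | 78.6 -> 77.2 (-1.4) |
| 0.10 | 80.5 -> 83.2 (+2.7) | 80.3 -> 82.0 (+1.7) | 78.8 -> 81.2 (+2.4) |
| 0.30 | 83.0 -> 92.0 (+9.0) | 82.5 -> 90.6 (+8.1) | 78.6 -> 90.0 (+11.4) |

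So the power gain does not need blocking. The conservatism does: at R2 0.30 the t-test's type I error was 2.3% with blocks of 4 and 4.7% when allocation was not balanced within strata.

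**Baseline volume.** It is not a stratification factor. When it alone predicted outcome (R2 0.30), the t-test's type I error was 5.0%, so omitting it does not make the test conservative. It costs power only if volume predicts percent change.

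**Skewed outcome.** Here the volume ratio is log-normal, with blocks of 4, 80 complete patients and invented covariate effects. Entries are power, t-test -> t-test plus strata.

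| Assumed effects | Log SD 0.5 | Log SD 1.0 (strong skew) |
|---|---|---|
| None | 83.2 -> 83.0 (-0.2) | 68.8 -> 68.5 (-0.3) |
| Small | 78.1 -> 80.2 (+2.1) | 68.4 -> 68.8 (+0.4) |
| Moderate | 63.9 -> 72.3 (+8.4) | 63.2 -> 65.0 (+1.8) |
| Strong | 36.9 -> 52.7 (+15.8) | 49.4 -> 54.1 (+4.7) |

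At log SD 1.0, adding log baseline volume to the strata moved power from 68.8 to 68.3% (small effects) and left it at 65.0% (moderate).

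**Interim, N = 20.** A fuller model with six strata plus baseline cut power from 74% to 64% (blocked), or to 54% (simple randomisation), when nothing was prognostic.

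**Order of the Baseline visit (section 3.2.1).** Step 5 stratifies and randomises, then documents the ulcer. Debridement, if needed, uses the assigned product, and size is measured after debridement. Stage appears again in the wound description that follows. As written, baseline volume and that second Stage record can therefore post-date open-label allocation and exposure to study product.

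**The case against.** The strongest reply is that a t-test after randomisation is valid, that adjustment is good practice rather than an obligation, and that the size of the gain rests on values the documents do not give. All of this stands, and it is why the point concerns efficiency only. The largest gains above need strong covariate effects with modest skew, and nothing in the documents supports effects of that size.

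A second reply is that section 6.3.1 already promises stratified efficacy results and allows regression. A reader might infer that the plan ignores the strata altogether; it does not. But the promise can mean by-stratum summaries or a stratified test, and the named test remains the t-test.

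Three stronger readings should also be set aside:

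- **False positives are inflated.** They are not; the t-test's error rate was at or below about 5% in these calculations.
- **Omitting baseline volume makes the test conservative.** It does not, because volume was not stratified on.
- **Adding baseline volume is a free gain.** The visit order makes it a doubtful pre-treatment covariate, and no passage says that it predicts percent change. The same value is already the denominator of percent change, so the t-test shares that exposure; this is no reason to add it again as a covariate.

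**Conclusion.** The point holds as a recommended improvement. The primary test leaves the randomisation factors unused, and no pooled or adjusted test is defined elsewhere. If the strata are prognostic, power is lost; if allocation is also balanced within them, the test is conservative.

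Under a roughly normal outcome at N = 80, adjusting for the strata changes power by about -2 to 0 points if nothing is prognostic, +2 to +3 at strata R2 0.10, and +9 to +10 at 0.30 (+8 to +11 across the individual runs shown). With strong skew and small or moderate effects the change is under 2 points. The R2 values, effect size, allocation ratio, blocking and outcome distributions are all assumptions, so the true loss in this trial cannot be stated.

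**What to change.** In section 6.3.1 and the synopsis, pre-specify for the final analysis: 'Percent change in wound volume is compared between arms by a linear model with treatment, smoking status and study ulcer Stage, both exactly as used in the randomisation list. The adjusted mean difference is reported with its 95% confidence interval.'

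Also:

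- State which smoking levels form the strata, and how allocation is balanced within them.
- Use the Stage on which the patient was stratified, not the one in the later wound description.
- Keep the unadjusted t-test as a sensitivity analysis.
- State that by-stratum results are descriptive.
- Leave the interim t-test (about 20 patients) unchanged, because extra terms can cost power there.
- Add log baseline volume to the primary model only if it is recorded before allocation and before any use of study product. Otherwise use it only in a sensitivity analysis.

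The cost is a few sentences and a few lines of code. Both factors are already recorded, and the target remains the mean difference in percent change. The downside is about 1 to 2 points of power if the covariates are not prognostic.

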Study Period:	Enrollment Period: Rolling enrollment to the earliest of 2 years or enrollment of 80 subjects Treatment Period: Baseline (Week 0) to Final Evaluation (earlier of 6 months = Week 24 or complete wound closure) Analysis Period: An interim analysis will be conducted when the greater of 20 patients or those enrolled in the two (2) weeks following enrollment of the first participant have completed the Week 12 visit. The full analysis is when all subjects have completed the Final Evaluation.
Phase of Development:	Post-marketing
Objective:	A pressure ulcer (wound/sore) is localized injury to the skin and/or underlying tissue usually over a bony prominence, as a result of pressure, or pressure in combination with shear and/or friction. Primary objective: To compare percentage change in ulcer size in patients with at least one Stage III or Stage IV pressure ulcer in subjects treated with Microcyn versus sterile saline. Secondary objectives: To compare healing progress using the National Pressure Ulcer Advisory Panel’s Pressure Ulcer Scale for Healing (PUSH) score, Version 3.0, and other indicators of wound healing such as time to complete wound closure, elimination of signs of wound infection and to investigate the impact of treatment with Microcyn on subject health care resource utilization (wound-related).
Clinical Hypothesis:	

Name of Sponsor/Company:	Oculus Innovative Sciences, Inc.
Name of Finished Product:	Microcyn [®] Skin and Wound Care with preservatives (“Microcyn”)
Name of Active Ingredient:	N/A
Treatment of pressure ulcers with Microcyn results in faster healing and better overall outcomes than treatment with sterile saline in spinal cord injured adults.	
Design and Methodology:	
Design: Six month (24 week), randomized, open-label, comparative study of treatment of pressure ulcers using Microcyn versus sterile saline.	
Subjects: Adults with spinal cord injuries with at least one Stage III or Stage IV pressure ulcer who meet all eligibility criteria and who have given informed consent.	
Treatment: Microcyn or sterile saline liberally sprayed on wound and permitted to remain on wound which will then be dressed with gauze that is moistened with Microcyn or sterile saline and covered with dry gauze twice daily for the earlier of total wound closure or Week 24.	

Study Visits:

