Overall: Assessments will be made at Week 0 (Baseline) with follow-up visits every 4 weeks thereafter, for a total of up to 7 study related assessments (Week 0 (Baseline), Weeks 4, 8, 12, 16, 20 and Week 24 (Final Evaluation)). Subjects will return to the clinic for all follow-up assessments.

Baseline: Initial demographics and a brief medical history will be collected at Baseline from subjects or via chart abstraction after informed consent and after meeting all inclusion/exclusion criteria. Data on the primary endpoint will be collected: pressure ulcer size (stage, length, width, and depth) via clinician measurement with photographic documentation. Secondary endpoints of infection status of the ulcer including signs/symptoms of infection, amount and type of exudates, color and type of tissue/character of the wound bed and health care resource utilization (wound-related) and adverse events will also be collected at Baseline. The wound surface area (length x width), amount of exudate and tissue type will be recorded using the PUSH Tool 3.0, and a PUSH baseline score will be calculated (PUSH score).

Follow-up visits: Information collected at each follow up visit will include information on the pressure ulcer size (length, width, depth via clinician measurement with photographic documentation), PUSH sub-scores and total score, time to complete closure of wound, infection status of the ulcer including signs/symptoms of infection, health care resource utilization (wound-related) and adverse events. If applicable, reason for early discontinuation will be recorded. Treatment-related adverse events will be collected at all follow-up visits.

Procedures	Baseline	Follow-Ups	Final Evaluation
Study procedures			
Informed Consent and Privacy Authorization	X		
Inclusion/Exclusion Criteria	X		
Demographics			
Age, Race, Gender, Education, Insurance Status (from chart)	X		
Marital, Employment, Insurance Status			
Medical History			
Height, Weight, Smoking/Tobacco Status	X		
Spinal Cord Injury Information (from chart)	X		
Type of Bladder Management	X		
Number of Concomitant Ulcers	X	X	X
Use of Antibiotics	X	X	X
Primary efficacy endpoint			
Ulcer Depth, Length, Width, Stage	X	X	X
Secondary endpoints			
Wound Infection Status	X	X	X
Amount and Type of Exudate	X	X	X
Color/Type of Tissue/Character of Wound Bed	X	X	X
PUSH Scores	X	X	X
Health Care Resource Utilization (Wound-Related)		X	X
Safety			
Reason for Early Discontinuation (if applicable)		X	
Adverse Events	X	X	X

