5.1. DEFINITIONS

An adverse event is an unfavorable change in health, including abnormal laboratory findings, that occurs in trial participants during the clinical trial or within a specified period following the trial. For purposes of this Protocol, the specified period is Weeks 0-24 (per patient).

An MDR reportable event is one that reasonably suggests that a marketed device has or may have caused or contributed to a death, serious injury, or has malfunctioned, and that the device or a similar device marketed by the manufacturer would be likely to cause or contribute to a death or serious injury if the malfunction were to recur. Serious Adverse Events include adverse events that result in death, require either inpatient hospitalization or the prolongation of hospitalization, are life-threatening, result in a persistent or significant disability/incapacity or result in a congenital anomaly/birth defect. Other important medical events, based upon appropriate medical judgment, may also be considered Serious Adverse Events if a trial participant's health is at risk and intervention is required to prevent an outcome mentioned.

Serious injury/(serious illness) is an injury or illness that:

- is life threatening, even if temporary in nature;
- results in permanent impairment of a body function or permanent damage to a body structure; or
- necessitates medical or surgical intervention to preclude permanent impairment of a body function or permanent damage to a body structure.

A complaint is any written, electronic or oral communication that alleges deficiencies related to the identity, quality, durability, reliability, safety, effectiveness, or performance of a device after it is released for distribution.

A malfunction is a failure of the device to meet its performance specifications or otherwise perform as intended. Performance specifications include all claims made in the labeling for the device. A reportable malfunction is a malfunction for which:

- the chance of a death or serious injury resulting from a recurrence of the malfunction is **not** remote;
- the consequences of the malfunction affect the device in a catastrophic manner that may lead to a death or serious injury;
- the malfunction causes the device to fail to perform its essential function and compromises the device's therapeutic, monitoring or diagnostic effectiveness which could cause or contribute to a death or serious injury, or other significant adverse device experiences; or

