6. STATISTICAL ANALYSIS

6.1. GENERAL CONSIDERATIONS

All statistical programming will be performed using SAS version 9.1 or higher, or similar statistical program. Statistical significance will be based on two-sided tests at the 5% level of significance. There are two planned analyses. The first will be conducted when the greater of 20 patients or those enrolled in the two (2) weeks following enrollment of the first participant have completed the Week 12 assessments. The second will be when all 80 patients have completed the Week 24 (Final Evaluation) assessments.

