6.3.2. SAFETY

Adverse event analyses will be conducted for the interim and final analyses. Safety analyses will be conducted via Fischer's exact tests, chi-square, and t-tests, as applicable. The safety population will include all subjects exposed to the study product who have provided any post-treatment safety information.

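### Adverse events and resource use are compared with no allowance for time observed, so unequal follow-up can pass for a treatment difference

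*Combined protocol and SAP*

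**What the plan says.** **Length of follow-up.** The synopsis (Study Period) runs treatment from "Baseline (Week 0) to Final Evaluation (earlier of 6 months = Week 24 or complete wound closure" and plans visits "for a total of up to 7 study related assessments". Section 2.1.4 stops application at the same point. Section 3.2.5 calls an exit early only if it comes before the earlier of closure or Week 24, so closure counts as a normal end. The same section allows withdrawal at any time without replacement, and section 4 disenrols a patient who starts a prohibited treatment.

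**Text pointing the other way.** For adverse events, section 5.1 states that "the specified period is Weeks 0-24 (per patient". Section 3.2.2 lists visits through Week 24 with no exception for healed patients, and section 6.1 times the final analysis by the Week 24 assessments of all 80 patients.

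**Analysis.** Resource use: "Number and health care resource utilization (wound-related) will be tallied and compared between Microcyn and saline" (section 6.3.1). Adverse events: Fisher's "exact tests, chi-square, and t-tests, as applicable" (section 6.3.2). The safety population in section 6.2 admits anyone exposed who gave any safety information after treatment, however short the follow-up. Only closure has a time-based method (Kaplan-Meier, section 6.3.1).

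**What is recorded for resource use.** Section 3.2.2, item 4, asks for the number of visits and then for items such as home care orders, mattress, medication and seating evaluation, which are essentially yes/no.

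**The concern.** A patient observed for 8 weeks has less opportunity to report an adverse event or a clinic visit than one observed for 24. A tally, or a test on the proportion with an event, treats the two alike. If follow-up is shorter in one arm, that arm shows fewer events even when the weekly risk is identical.

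Two mechanisms could make follow-up unequal, and they can push in opposite directions. Faster closure shortens observation in the better-healing arm and makes it look safer. More withdrawal or disenrolment shortens observation in the arm that loses patients and makes that arm look safer and less costly. The trial is open-label, so exits may well differ by arm. What is at stake is whether a difference in safety or resource use reflects the product or only who stayed longer.

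**Working it through.** The plan has no figure to reproduce. Its sample size statement reads "The sample is a convenience sample of 80 patients", and it gives no adverse event, closure or withdrawal rate. All rates below are assumptions. The allocation ratio is not stated either ("Following stratification, patients will be randomized to study product (Microcyn or sterile saline"), so 40 per arm is assumed.

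**Step 1: expected counts at equal weekly rates.** If a share c of an arm leaves observation at Week w and the rest stay to Week 24, mean follow-up is (1 − c) × 24 + c × w. With the same weekly rate in both arms, the ratio of expected counts equals the ratio of mean follow-up.

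| Assumption | Arm with more exits (weeks) | Arm with fewer exits (weeks) | Ratio |
|---|---|---|---|
| 10% vs 5% close at Week 12 | 0.90×24 + 0.10×12 = 22.8 | 0.95×24 + 0.05×12 = 23.4 | 0.974 (3% fewer) |
| 30% vs 15% close at Week 14 | 0.70×24 + 0.30×14 = 21.0 | 0.85×24 + 0.15×14 = 22.5 | 0.93 (7% fewer) |
| 40% vs 20% close at Week 12 | 0.60×24 + 0.40×12 = 19.2 | 0.80×24 + 0.20×12 = 21.6 | 0.89 (11% fewer) |
| 50% vs 25% close at Week 12 | 0.50×24 + 0.50×12 = 18.0 | 0.75×24 + 0.25×12 = 21.0 | 0.86 (14% fewer) |
| 30% vs 10% withdraw at Week 8 | 0.70×24 + 0.30×8 = 19.2 | 0.90×24 + 0.10×8 = 22.4 | 0.86 (14% fewer) |

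The closure rows apply to adverse events, and only if observation stops at closure. The withdrawal row applies to both outcomes. The low-closure row is plausible: section 1 cites a retrospective study in which over 50% of ulcers had not fully healed in three years.

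**Step 2: the scale Fisher's test uses.** The proportion with at least one event is 1 − [(1 − c)·exp(−24r) + c·exp(−w·r)] for weekly rate r. For 40% versus 20% closing at Week 12:

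- r = 0.05: 1 − (0.6×0.301 + 0.4×0.549) = 60.0%, against 1 − (0.8×0.301 + 0.2×0.549) = 64.9%.
- r = 0.10: 82.5% against 86.7%.

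That is 4 to 5 percentage points, or about two patients in an arm of 40.

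**Step 3: false positives.** Section 6.1 sets the level: "Statistical significance will be based on two-sided tests at the 5% level of significance". A simulation used 2000 runs per scenario, 40 per arm, exponential closure and withdrawal times capped at Week 24, and Poisson events at the same weekly rate in both arms, so every rejection is false. It took the t-test to be applied to event counts. Simulation error near 5% is about √(0.05×0.95/2000) = 0.5 percentage points.

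- Time to closure 26% shorter in one arm (the interim threshold in section 6.3.1, borrowed for illustration), slower arm closing 10% to 70%, no withdrawal: t-test 5%–11%, Fisher 2%–6%. At 30% versus 38% closing, t-test 5.5%–6.0% and Fisher 3%–4%.
- 20% versus 50% closing: t-test 14%–36%, Fisher 7%–14%, over 0.05–0.25 events per week.
- 30% versus 70% closing: 45% and 33% at 0.10 per week; the t-test reaches 66% at 0.25.
- Withdrawal of 40% versus 10%, no closure, 0.10 per week: 21% and 16%.
- 30% versus 38% closing combined with 40% versus 10% withdrawing, the larger loss in the slower-healing arm: t-test 7%–9%, Fisher 5%–6%, because the mechanisms partly cancel.
- A test of events per patient-week stays at 4.0%–5.2% in every scenario. Exit in these runs was independent of adverse events, so this is a favourable case for that test.

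**The case against.** **Observation may not stop at closure.** Sections 5.1, 3.2.2 and 6.1 can be read as following everyone to Week 24. If so, the closure part of the adverse event argument disappears. This stands to the extent that the documents conflict. A reader might infer that adverse event observation certainly ends at closure, and the text does not settle that. Nor does it settle the reverse. Section 5.2 collects adverse events at scheduled visits, and no visit after closure is described. Section 5.5.2 covers only new serious events, judged associated with the product, after the last scheduled contact. The synopsis defines the Final Evaluation as the earlier of closure or Week 24, so the reference to it in section 6.1 does not clearly require healed patients to return.

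**Less use after healing is the benefit sought.** This stands for resource use. A reader might infer that every shortfall in resource use is an artefact, but lower use once the study ulcer has closed is what the secondary objective looks for, and dividing by time to closure would hide it. It holds partly for adverse events too: application stops at closure, so fewer application-related events can be a real consequence of faster healing. A weekly rate and a cumulative proportion answer different questions, which is a reason to report both.

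**The method is unspecified, not wrong.** For resource use this is fair: a tally does not rule out adjustment. For adverse events, the qualifier in section 6.3.2 chooses among three named tests, none of which uses time observed.

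**The effect is small.** This stands for low or moderate closure and similar withdrawal. Incidence with Fisher's test is also a usual summary.

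**Conclusion.** The concern holds in a limited form. Follow-up can differ by patient and by arm, and neither adverse events nor resource use has a rule for it, so unequal follow-up can be read as a treatment difference in either direction. Under the assumed rates, expected adverse events differ by about 3% to 14% at the same weekly risk. Fisher's test is little affected unless closure or withdrawal differs greatly between arms.

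A reader might go further and infer that the safety comparison is bound to be misleading, or to favour Microcyn. The documents do not support that: they give no rates, the direction depends on which mechanism dominates, and the two can partly cancel. Severity is minor to moderate, because neither outcome is primary and the stopping rule in section 6.3.1 rests on time to closure.

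**What to change.** 1. **Observation window.** Reconcile the synopsis (Study Period) and sections 3.2.5, 5.1 and 6.1 into one stated adverse event window, and say whether healed patients are followed after closure.
2. **Section 6.3.2.** Keep Fisher's test. Add adverse events per patient-week observed, compared by Poisson or negative binomial regression with log weeks as offset, or by time to first event. State that an offset corrects for length of follow-up but not for exit that depends on outcome, such as withdrawal because of an adverse event.
3. **Exit date.** Record it. Section 8.1 lists visit dates, but sections 3.2.2, 3.2.5 and 4 ask for the reason for leaving, not its date.
4. **Section 6.3.1, visits.** Compare the number of wound-related visits as a total to Week 24. Treat study-ulcer use after closure as zero, state this as an assumption, and add a sensitivity analysis for other wounds or recurrence. Use an offset only for time lost to withdrawal or disenrolment.
5. **Section 6.3.1, yes/no items.** Compare these as proportions; they are not weekly counts.

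The cost is analysis wording, one recorded date and slightly more programming. The downside is reliance on the zero-use assumption, which is an imputation because patients may have other ulcers.
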